**Table 14 – guidance for collecting follow-up data**

Outcome	Process
Outcome one: Woman and Infant are discharged home with no significant health concerns.	
 
At six weeks screen the hospital electronic records for notification of an infant death.             
 
No notification of infant death - invite or prompt woman to complete the two-month follow-up for herself and her infant.
 
Notification of infant death – Do not make further contact with the family.
 
 
 
If no notification of infant death at six weeks check the hospital records at 22 weeks for subsequent notification of infant death.             
 
No notification of infant death - invite or prompt woman to complete the six-month follow-up for herself and her infant.
 
Notification of infant death – Do not make further contact with the family.
 
 
 

Outcome two:  Woman discharged home and her infant is stillborn or died in hospital.	
 
Do not make further contact with the family.
 

Outcome three:  Woman discharged home but her infant has serious health concerns or is receiving palliative care.	
 
At six and 22 weeks using hospital number check electronic participant records for notification of an infant death - undertake a detailed review of the hospital case notes, follow-up any transfers to other hospitals / hospice or contact the infant's neonatologist prior to prompting or sending two and six months questionnaires.             
 
No notification of infant death - invite or prompt woman to complete the two-month follow-up for herself and her infant.
 
Notification of infant death – Do not make further contact with the family.
 
No notification of infant death - invite or prompt woman to complete the six-month follow-up for herself and her infant.
 
 
 

	Notification of infant death - Do not make further contact with the family.
Outcome four: 	
Woman discharged home but her infant has significant health concerns for which they are receiving treatment.
 
 
At six and 22 weeks using hospital number check electronic participant records for notification of an infant death - undertake a detailed review of the hospital case notes, follow-up any transfers to other hospitals / hospice or contact the infant's neonatologist prior to prompting or sending two and six months questionnaires.             
 
No notification of infant death - invite or prompt women to complete the two-month follow-up for herself and her infant.
 
Notification of infant death – Do not make further contact with the family.
 
 
 

Outcome five: 	
Women discharged home but her infant has significant health concerns and remains in hospital at two and / or six months.
 
For the woman
 
 
At six weeks telephone contact first, to discuss completing the two-month follow-up for herself. Ask permission to make contact again for the six month follow-up – record decision.
 
At 22 weeks telephone contact first, to discuss completing the two-month follow-up for herself.
 
 
For the infant
 
 
The research midwife will collect the data.
 

Outcome six: Infant discharged home no significant health concerns. Residence different from mother.	
 
At six weeks check the hospital records for notification of an infant death.             
 
No notification of infant death - invite or prompt guardian / adoptive parent to complete the two-month follow-up for the infant.
 
Notification of infant death - Do not make further contact with the guardian or adoptive family.
 
 
 
If no notification of infant death at six weeks check the hospital records at 22 weeks for subsequent notification of infant death.             
 
No notification of infant death - invite or prompt guardian / adoptive parent to complete the two-month follow-up for the infant.
 
Notification of infant death - Do not make further contact with the guardian or adoptive family.
 
 
 

Outcome seven: 	
Women discharged home to residence different from infant.
 
 
At six weeks telephone contact first, to discuss completing the two-month follow-up for herself. Ask permission to make contact again for the six month follow-up – record decision.
 
At 22 weeks telephone contact first, to discuss completing the two-month follow-up for herself.
 

Outcome eight: 	
 
Do not make further contact with the family.
 

In-hospital maternal death and infant discharged home with / without significant health concerns.	
---	--

 Indicates particularly sensitive or distressing outcome which requires specialist contact

If any core data items are missing from a participants follow up questionnaire, attempts will be made to contact the participant to collect these in accordance with the procedure stated in the data management plan.

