#### 2.9.2.3 Longer term outcomes:

Women's physical and psychological health and satisfaction with delivery:

- Experience; six simple questions (SSQ) at two months
- Duration of exclusive breast feeding at two and six months
- Health-related quality of life (EQ-5D-5L) at baseline\*, two and six months (appropriate licences to allow reproduction of these questionnaires will be obtained)
- Edinburgh post-natal depression scale at baseline\*, two and six months
- Impact of Events Scale two months
- Post-partum bonding questionnaire at two months
- Maternal report of infant health at two and six months
- Urinary incontinence ICIQ-UI short form assessed at baseline\*, two and six months
- Faecal incontinence assessed at baseline\*, two and six months
- Sexual function at baseline and six months
- Maternal and infant death at six months from HES-ONS linked mortality data. Obtain if the six month follow-up is not completed.
- Participant health resource used for economic analysis for mother and baby at two and six months

All participants will be asked to complete questionnaires, at two and six months post delivery, if they have not previously withdrawn. Participants will receive reminders to complete the questionnaires, either by text or email. If participants have not responded to the questionnaires within 6 weeks of the first questionnaire being sent to the participant, efforts will be made to collect a core set of data by telephone. These core data will include:

- Breastfeeding status at two and six months
- Health-related quality of life (EQ-5D-5L) at two and six months
- Maternal report of infant health at two and six months
- Maternal report of her own health at two and six months

\* Within the cohort, only women who deliver by planned caesarean section are required to complete baseline patient reported outcome measure questionnaires

Responses from the Two Month Questionnaire will be reviewed to identify babies who have potentially sustained harm relating to a birth injury. We will request relevant data from site for those babies identified and, blind to treatment allocation, an adjudication committee will classify these as delivery related/not delivery related and for those that are delivery related those likely to have a substantial long term impact and those that are minor or likely to be short lived.

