Overall there are 5.61 perinatal deaths per 1,000 total births up to 28 days post-delivery, comprising 3.87 stillbirths and 1.74 neonatal deaths; in our study this equates to 22.44 infants in the randomised study (N=4,000) and 3.41 infants in the cohort study for women having an elective section. These figures are an overestimate of the likely number of perinatal

deaths during this trial, because these figures include infants from 24+0 weeks and in this study the earliest a women can enter the trial process is 28+0 weeks. Whilst these are rare occurrences, they are extremely distressing, and can have long term psychological consequences for the mother such as anxiety and depression.

It is important that in the conduct of this trial, we act to minimise distress for participants and their families; to achieve this we will do the following

- Check the hospital electronic record system for notification of neonatal death in all infants participating in the study who were discharged home, prior to prompting or contacting women about completing two and six month follow-up.
- Where a neonatal death is recorded, we will liaise with hospital bereavement service to determine if the woman is known to them, if she is, the first contact will come from a member of the hospital bereavement service; if not, the first contact will come from the research midwife or an experienced member of the research team. In all cases the first contact will be personal, by telephone;
- We will develop 'outcome specific questionnaires' so women will only receive questionnaires specific to their circumstances (table 12) i.e. women whose infant has died will not receive prompts or follow-up infant questionnaires;
- We will develop outcome specific guidance to support the trial team in collecting follow-up data; we have red-flagged outcomes that are particularly sensitive or distressing.

There are routine NHS data that will provide information on deaths. However, the time taken in accessing these data is disproportionate when compared to the follow-up time intervals of interest for this study.

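### Table 14 names the two-month follow-up at the 22-week step in outcomes five, six and seven and lists no six-month invitation in outcome four, against section 2.9.2.3

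*Protocol*

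**What the plan says.** Section 2.9.2.3 sets the general rule: "All participants will be asked to complete questionnaires, at two and six months post delivery", unless they have already withdrawn. Table 14 in section 5.2 then gives staff a pathway for each of eight situations after birth.

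- **Outcome five** (mother home, infant still in hospital at two and/or six months). At six weeks the mother is telephoned about the two-month follow-up, and staff are told: "Ask permission to make contact again for the six month follow-up". At 22 weeks: "At 22 weeks telephone contact first, to discuss completing the two-month follow-up for herself". For the infant: "The research midwife will collect the data", with no time point.
- **Outcome six** (healthy infant living apart from the mother). After the 22-week record check, if there is no notification "of infant death - invite or prompt guardian / adoptive parent to complete the two-month follow-up for the infant".
- **Outcome seven** (mother living apart from the infant). The six-week and 22-week steps for the mother are worded as in outcome five.
- **Outcome four** (infant at home and under treatment). The lead-in calls for record checks at six and 22 weeks "prior to prompting or sending two and six months questionnaires". The only invitation listed below it is for the two-month follow-up.

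On bereavement, a bullet in section 5.2 describes what happens when a neonatal death is recorded. The hospital bereavement service makes the first contact if it knows the woman; otherwise the research midwife or an experienced team member does. It adds: "In all cases the first contact will be personal, by telephone". Table 14, on notification of an infant death, says: "Do not make further contact with the family". Section 2.9.2.3 says only that no questionnaires go to a bereaved family.

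**The concern.** Three rows send staff back at 22 weeks for a questionnaire already raised at six weeks, and a fourth lists no invitation to the six-month one. Section 5.2 describes outcome-specific guidance to support the team collecting follow-up, and Table 14 carries that guidance, so its wording may be applied as it stands.

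For the women, the six-month items in section 2.9.2.3 are at stake: EQ-5D-5L, the Edinburgh depression scale, exclusive breastfeeding, urinary and faecal incontinence, sexual function and resource use. Sexual function is measured only at baseline and six months, so a missed six-month questionnaire leaves no post-delivery value. The maternal report of infant health at six months is also a secondary outcome. Section 6.7 uses the two- and six-month economic questionnaires to populate the decision model.

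The families concerned are not a random subset. They have an infant under treatment, an infant still in hospital, or a mother and infant living apart.

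The bereavement wording is a separate matter. Staff have two instructions for the same event, in a section whose stated aim is to minimise distress.

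**Working it through.** No rate, power or sample size enters this point. The check is a reading of the rows side by side, plus one piece of timing arithmetic.

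**1. Which follow-up can a 22-week step serve?** Months = weeks × 7 / 30.44.

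- 6 weeks: 42 / 30.44 = 1.4 months. Two months is 2 × 30.44 / 7 = 8.7 weeks, so this step falls 2.7 weeks before the two-month point.
- 22 weeks: 154 / 30.44 = 5.1 months. Six months is 6 × 30.44 / 7 = 26.1 weeks, so this step falls 4.1 weeks before the six-month point and 13.3 weeks after the two-month point.

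The 22-week step makes sense only as the lead-in to the six-month follow-up, as outcome one uses it.

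**2. Rows of Table 14.**

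| Outcome | Whose follow-up | Later step names | Consistent with 2.9.2.3? |
|---|---|---|---|
| One | Woman and infant | Six-month | Yes |
| Two | None (stillbirth or death in hospital) | – | Not applicable |
| Three | Woman and infant (serious concerns or palliative care) | Six-month | Yes |
| Four | Woman and infant | Both in the lead-in; two-month only in the invitation | Invitation missing |
| Five | Woman (infant via research midwife) | Two-month | No |
| Six | Infant, via guardian | Two-month | No |
| Seven | Woman | Two-month | No |
| Eight | None (maternal death) | – | Not applicable |

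Six of the eight rows involve follow-up. Two name the six-month invitation, three name the wrong follow-up, and one omits the invitation. Outcome three has the same lead-in as outcome four and does list the six-month invitation, so the omission in outcome four is not house style.

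**3. Internal consistency.** Outcomes five and seven ask at six weeks for permission to make a six-month contact. The next line then describes a contact about the two-month follow-up.

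**4. Is there an exemption?** Footnote 4 to Table 8 releases only cohort women not planning a caesarean section from the two- and six-month follow-up. Section 2.9.2.3 stops questionnaires only for bereaved families. Neither covers outcomes four to seven.

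**5. Would another step catch a missed questionnaire?** Under section 2.9.2.3, telephone collection of core data starts when there is no response within six weeks of sending, so an unsent questionnaire does not clearly trigger it. The core set also leaves out the depression scale, incontinence and sexual function. The note after Table 14 on chasing missing core items starts from the participant's follow-up questionnaire. The HES-ONS linkage gives deaths only.

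**6. Bereavement.** Outcome one covers an infant who went home and whose death is later notified. The section 5.2 bullets cover the same event, since the record check there is of infants discharged home. One text provides for a personal call and the other for no further contact.

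**The case against.** The strongest reply is that this is a copy error which staff would recognise. Section 2.9.2.3 governs, Table 14 is headed as guidance, Table 15 repeats follow-up at two and six months, and outcomes five and seven themselves ask permission for the six-month contact. That stands as far as it goes: loss is a risk if the table is followed literally, not a demonstrated consequence. It does not remove the contradiction.

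A reader might infer several stronger things that the document does not support:

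- **That the six-month questionnaire is never mentioned in outcome four.** The lead-in mentions it. Only the invitation step is missing.
- **That six-month data are lost for the sickest infants.** Outcome three, covering serious concerns and palliative care, is correct. In outcome five the infant's data come from the research midwife. Outcome six concerns infants without significant health concerns.
- **That four pathways lose every six-month outcome.** Outcomes five and seven affect only the woman's own data, and outcome six only the guardian's report on the infant. Outcomes six and seven may also be two sides of one situation.
- **That multiple imputation would fail.** Loss tied to infant condition or separation could be informative, but nothing in the protocol shows that it would be beyond repair by imputation.

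On bereavement, it can be said that the Table 14 instruction means no further contact for follow-up purposes, which could coexist with a bereavement call. That reading is possible, but the table does not state it. The rule in section 2.9.2.3 does not settle the matter because it bars only questionnaires, not contact.

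**Conclusion.** The point holds as an inconsistency in operational instructions. Table 14 names the wrong follow-up at 22 weeks in outcomes five, six and seven, and lacks the six-month invitation in outcome four. This contradicts section 2.9.2.3, the 22-week step in outcome one and, in outcomes five and seven, the rows' own permission request.

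If the table is followed literally, six-month secondary and economic data could be missed for the women in outcomes four, five and seven. Infant reports at six months could be missed in outcome six and possibly outcome four. The protocol gives no number for these groups, so the size cannot be stated, and whether any loss would differ by arm cannot be judged. The primary outcome is not affected. The conclusion assumes that staff work from Table 14; if they work from section 2.9.2.3, little or nothing is lost.

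The separate inconsistency on contact after a recorded neonatal death, between the text of section 5.2 and Table 14, is also real and needs reconciling.

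**What to change.** In Table 14:

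1. In outcomes five and seven, make the 22-week step refer to the six-month follow-up for the woman, subject to the permission recorded at six weeks.
2. In outcome six, make the 22-week invitation to the guardian refer to the six-month follow-up for the infant.
3. In outcome four, add the six-month invitation step, as in outcome three.

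Separately, reconcile the section 5.2 text on personal telephone contact after a recorded neonatal death with the no-contact instruction in Table 14, noting that section 2.9.2.3 excludes questionnaires only. Which contact rule applies is for the trial team to decide.

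The cost is a wording change to the protocol and any work instructions drawn from it. No outcome, questionnaire or sample size changes. If follow-up has already begun, check whether families in outcomes four to seven were sent the six-month questionnaire.

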### 5.3 Database

The database will be developed by the Programming Team at WCTU. All specifications (i.e. database variables, validation checks, screens) will be agreed between the programmers and appropriate trial staff.

### 5.4 Data storage

All study related documentation and data will be stored in accordance with all applicable regulatory requirements and access restricted to authorised personnel. Data will be stored on the University of Warwick secure servers hosted in an on-premises data centre. Sharing of electronic data between the University of Warwick and PNI will be in accordance with WCTU SOP 15 part 3 'Data Transfer' and require data sharing agreements to be in place. Participants will provide consent to their data being shared with PNI as detailed in the consent form.

### 5.5 Data archiving

The trial records and associated documentation of the 4,000 randomised participants (women and infants) will be archived for 25 years; the trial records and associated documentation of the anticipated 3000 participants in the cohort study will be archived for 10 years (WCTU SOP 23 'Data Archiving'). Data collected within the Big Baby Study may be important resource for future research. For example, exploring the long-term effects for children with brachial plexus injury, as there is anecdotal evidence of an association between brachial plexus injury and epilepsy. To allow for such future research we will:

1. Contact the children of mothers enrolled in the randomised trial when they are aged 16-18 to ask for permission to keep their data and contact details for future research; if at that time no further research is planned we will not approach for consent to use data for future research. We will only approach those for whom we have obtained consent for further research. All data for which we do not have consent to keep will be destroyed after 25 years. We are here drawing a distinction between the archived data relating to the completed trial and the permission to the active use of data we hold for the purposes of future research.
2. For the children of mothers enrolled in the cohort study we will first make a decision after ten years as to whether there are important future research questions that can be addressed by approaching this group again. If no further work is anticipated we will destroy the data. If future work is planned then we will keep the data until children are aged 16-18 and approached them at this time to keep their data for future research. If we do not have consent to keep the data it will be destroyed at this time.

In order to be able to contact children born within the study in the future we will use data held by NHS digital (or any successor organisation) to obtain their contact details.

## 6. DATA ANALYSIS

### 6.1 Statistical analysis

All analyses will be by intention to treat at the time of randomisation. Not all women will have a vaginal delivery as planned. We will therefore collect numbers having a caesarean section broken down by type/indication as defined using the Robson score. A detailed statistical analysis plan will be developed by the trial statisticians and approved by the TSC and DM(E)C.

Our primary analysis will be based on the assessment of the incidence of shoulder dystocia between intervention and control. Comparison between the intervention groups will be made using logistic regression models both adjusted and unadjusted using appropriate covariates. Other secondary binary outcomes will be analysed in a similar way. Continuous outcomes will be analysed using linear regression models; again both adjusted and unadjusted analyses will be computed. Non-compliance will be taken into account using a CACE (Complier Average Causal Effect) analysis and if required, sensitivity analyses will be computed (for example, assessment of missing data using multiple imputation).

### 6.2 Interim analysis

We will conduct key event analysis after data are available on 1,000 participants. This will allow the DM(E)C to make recommendations about adjustment to the target sample size in the light of data on recruitment and outcome incidence, and to consider continuation of recruitment, taking into account early data on the observed differences between the groups and safety information.

While we have designated a 'primary' outcome, understanding the effect of induction for macrosomia is far more nuanced than simply whether it affects the process measure of shoulder dystocia. It is important to determine whether it has any impact on the primary target of the intervention, but effects on other outcomes will affect interpretation of the findings; for example, if we find a reduction in the incidence of shoulder dystocia, but no differences in fetal wellbeing outcomes and harm on one or more maternal outcome(s). Women and clinicians might here conclude that induction should not be recommended in spite of a positive effect on the primary outcome. We will work with our PPI group during the lifetime of the study to develop a better understanding of how we should interpret the findings and on the interpretation once the main analyses are available.

### 6.3 Subgroup analyses

We will conduct a pre-planned conventional subgroup analyses using an interaction term for two key variables; maternal body mass index and fetal weight centile. Additionally we will apply data mining techniques we have developed to describe sub-groups using multiple parameters in a previous IPD meta-analysis. These include recursive partitioning, adaptive peeling and a Bayesian approach. This will allow us to identify any combinations of baseline characteristics that might predict better or worse responses to induction. We will apply all

three methods to a random sample of half of the data and then validate any promising clinical predication rules identified in the second half of the sample.

